2.2 CRF Pages

Not all data will be analyzed in this analysis. Only select CRF pages for key safety and efficacy endpoint to support the Phase III protocol development are considered.

2.3 Unique Patient Identification

Patient number from the CRF does not uniquely identify individual patients. If a patient initially had bilateral treatment, then all data are captured under a single patient number. If a patient initially had unilateral treatment but subsequently had the procedure performed on the untreated eye, data for the newly treated eye were captured under a different patient number. If a patient completed the month 6 assessment and the investigator elected to perform the CXL procedure again, then all data for this repeated procedure are captured under a second patient number.

Sites will provide a list of paired patient numbers that can be used to map all data for each patient to be summarized appropriately.

Patients receiving subsequent CXL therapy were re-randomized. Therefore the subsequent treatment may differ from the initial randomized treatment given during the first procedure. Efficacy summarization will be by individual eye which can accommodate the differing treatments. Adjustments to the safety analysis will need to be considered since that is done overall rather than by individual eye.

3. GENERAL CONSIDERATIONS

3.1 Analysis Considerations

All statistical summaries and analyses will be performed using SAS[®] software (SAS Institute, Cary, North Carolina, USA). Only subjects in the appropriate analysis set will be included in summary statistics.

Continuous data will be summarized by treatment using descriptive statistics (number, mean, standard deviation [SD], minimum, median, and maximum). Categorical data will be summarized by treatment using frequency tables (number and percentage).

Summaries will be presented by randomized treatment (Group 1, Group 2, Group 3) to allow between treatment comparisons.

3.2 Analysis Sets

Populations for primary analyses of safety and efficacy are defined as follows.

3.2.1 Randomized and Treated

The randomized and treated analysis set includes all subjects randomized in the study and have a procedure performed on at least 1 eye prior to the official data lock for this ad hoc analysis. Analysis of the treated analysis set will be by treatment received in the primary eye.

3.2.2 Safety

The safety analysis set (SS) includes all subjects enrolled in the treated analysis set. Safety analysis will be performed using the Safety Analysis Set. Analysis of the SS will be performed by the treatment actually received as recorded on the CRF. Subjects with initial unilateral treatment that have a subsequent procedure may appear in the SS under different treatment groups if the subsequent treatment differs from the initial treatment.

3.2.3 Efficacy Analysis Set

The efficacy analysis set (EAS) population consists of all patients diagnosed with keratoconus, who do not have prior CK treatment, who do not have a prior corneal crosslinking procedure, and removed contact lenses per protocol as indicated on the CRF. Furthermore, patients must have a measure of change from baseline in at least one of the three efficacy endpoints. Analysis of efficacy endpoints will use the EAS. All EAS analyses will be performed by the treatment received as recorded on the CRF.

If the patient's diagnosis per-randomization does not correspond to the diagnosis captured on the medical history page or the diagnosis captured in the procedure page, that patient will be excluded from the EAS.

Determination of the efficacy analysis set may include utilization of patient lists provided by CXL if the criteria set for the EAS can't be directly determined from the CRF data.

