4. BASELINE CHARACTERISTICS AND SUBJECT DISPOSITION

Descriptive baseline summaries of continuous data will present the group mean, standard deviation, median, minima, and maxima. Descriptive summaries of discrete data will present the category counts as frequencies and percentages.

Summaries will be presented by treatment as recorded on the CRF. Any results presented by diagnosis will be based on diagnosis from medical history.

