4.1 Disposition of Subjects

A disposition summary will include

- Number of randomized and treated by primary and fellow eye
- Number of subjects in the Safety analysis set. Subjects may be included in more than one column of the second eye was treated under a different treatment group.
- Number and percentage of subjects with the procedure on the right eye (OD), the left eye (OS) or both eyes (OU) for initial treatment
- Number and percentage of patients that had subsequent CXL treatment on the fellow eye
- Number and percentage of subjects in the efficacy analysis set (EAS)
- Number and percentage of subjects ongoing (per protocol)
- Number and percentage of subjects completing study (at Month 6 per protocol)
- Number and percentage of subjects discontinuing study and the reasons for discontinuation

A subject will be considered discontinued if they have a record that from the end of study CRF page suggesting they did not complete study.

Disposition summaries will be presented by initial treatment received and diagnosis. Percentages will be based on the number of subjects randomized.

A listing of subject disposition will include the date of the procedure for each eye, study completion status, and reason for termination (if applicable).

A separate listing will be provided to identify patients that had re-treatment with CXL.

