5.1 Primary Efficacy Endpoint

The primary measure of efficacy is the mean change from baseline in LogMAR of Corrected Distance Visual Acuity (CDVA) in the Primary Eye at Month 12 for each treatment group. As supportive analysis to the primary endpoint, the mean change from baseline and treatment differences will be estimated at Month 3 and Month 6.

Separately for each timepoint, analysis of variance (ANOVA) will be used to obtain point estimates and CIs for the change from baseline in LogMAR CDVA for each group. ANOVA will also be used to obtain point estimates and CIs for all pairwise comparisons between the treatment arms. P-values may be provided for descriptive purposes only.

As a sensitivity analysis, separate point estimates and confidence intervals for treatment differences based on a two-sample t-tests for each pairwise comparison will be performed without assuming equal variances. Satterthwaite approximation for degrees of freedom will be used.

Other sensitivity analysis such as mixed models repeated measures to account for the longitudinal nature of the data may be considered in an ad hoc manner.

The primary analysis will be repeated for the Fellow eye.

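### SAP 3.2.3 puts every efficacy analysis, including the pairwise arm comparisons, by treatment received, against the randomised grouping in SAP 3.1; Tables 2.1 and 3 also carry opposite rules, and no output counts mismatches

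*SAP*

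**What the plan says.** The SAP gives its grouping rule in several places.

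- **SAP 3.1**, the general rule: "Summaries will be presented by randomized treatment (Group 1, Group 2, Group 3) to allow between treatment comparisons".
- **SAP 3.2.1**: "Analysis of the treated analysis set will be by treatment received in the primary eye".
- **SAP 3.2.2**: "Analysis of the SS will be performed by the treatment actually received as recorded on the CRF".
- **SAP 3.2.3**: "All EAS analyses will be performed by the treatment received as recorded on the CRF".
- **SAP 4**, opening text: "Summaries will be presented by treatment as recorded on the CRF".
- **SAP 4.1**: "Disposition summaries will be presented by initial treatment received and diagnosis. Percentages will be based on the number of subjects randomized".
- **SAP 4.2** puts demographics of the treated set by randomised group, and **SAP 4.3** does the same for the procedure summaries.
- **SAP 5.1**: "ANOVA will also be used to obtain point estimates and CIs for all pairwise comparisons between the treatment arms". It does not say whether an arm means the one assigned or the one received.

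Appendix B gives an analysis set for each output but no grouping. SAP 1.6, on changes from the protocol, does not mention grouping. Section 8 of the protocol includes all treated eyes without saying how they are grouped. SAP 3.3 uses no strata or covariates beyond defining the efficacy set. SAP 3.2.3.1 says that no hypotheses are tested and that the estimates are descriptive.

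**The concern.** Randomisation protects a comparison between arms only if eyes are counted in the arm to which they were assigned. Grouped by treatment received, an eye given a different exposure moves to another arm. If the reason for the change is related to prognosis, the difference between arms mixes the effect of exposure with selection. No covariate adjustment is planned that could offset this, and no listed output would show how often it happened.

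The practical stake is Phase 3 design. SAP section 1 says that these interim data are to help design that protocol and support a meeting with the regulator. There is also a programming problem: where two rules apply to one table, a programmer cannot satisfy both if any mismatch exists.

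**Working it through.** The plan states no figure on this point, so the check sets the rules side by side.

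| Output | Rule pointing to the assigned arm | Rule pointing to treatment received |
|---|---|---|
| Pairwise contrasts of SAP 5.1 (for example Table 4.1.2) | none specific | SAP 3.2.3 |
| Efficacy summary tables (4.1.1 to 6.3.1 series) | SAP 3.1, if it reaches efficacy | SAP 3.2.3 |
| Table 2.2, demographics, efficacy set | SAP 3.1, if it reaches this set | SAP 3.2.3 |
| Table 2.1, demographics, treated set | SAP 4.2 | SAP 3.2.1, SAP 4 |
| Table 3, procedures, Safety Analysis Set | SAP 4.3 | SAP 3.2.2, SAP 4 |
| Table 1, disposition | percentages over the number randomised (SAP 4.1) | columns by initial treatment received (SAP 4.1), SAP 3.2.1 |

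**Step 1: efficacy.** There are two readings. If the specific rule in 3.2.3 overrides the general rule in 3.1, efficacy has one clear rule, by treatment received, and the contrasts are not between randomised groups wherever assignment and receipt differ. If 3.1 applies as well, the summary tables and Table 2.2 have two rules. Both readings leave something to correct.

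**Step 2: Tables 2.1 and 3.** Here the opposition comes from sections written for those tables or their analysis sets, so it does not depend on how far 3.1 reaches. Nor does it depend on the opening text of SAP 4, because 3.2.1 and 3.2.2 refer to treatment received on their own.

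**Step 3: what would reveal a mismatch.** Count of Appendix B: Tables 1, 2.1, 2.2 and 3 make 4; CDVA 6 tables + 3 figures = 9; UCVA 6 + 3 = 9; K_max 9 + 3 = 12; adverse event tables 3; listings 3. Total 4 + 9 + 9 + 12 + 3 + 3 = 40, of which 9 + 9 + 12 = 30 are efficacy outputs (21 tables, 9 figures). None of the 40 is specified as a count of assigned against received arm.

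**Step 4: size of the effect.** Suppose a fraction p of the eyes in a received group were assigned elsewhere, and their expected change under that same exposure differs by δ from that of the other eyes in the group. The group mean then moves by p × δ. Eyes that left the group can move it in the same way. With no mismatches the shift is 0; with mismatches unrelated to prognosis, δ = 0 and it is again 0. The documents give neither p nor δ, so no figure can be calculated.

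**Step 5: can mismatches occur?** The study is open label. Under Protocol Appendix 3, staff set the irradiance with a knob and swipe a card labelled with the randomisation group. Protocol 6.2.4 allows a procedure to be recorded as interrupted or discontinued. Mismatches are therefore possible. Nothing in the documents shows that any occurred.

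**The case against.** The strongest answer is that the efficacy rule is clear and defensible. SAP 3.2.3 is specific and SAP 3.1 is general, so the specific rule governs. For choosing Phase 3 exposure settings, estimates by exposure delivered are useful, and SAP 3.2.3.1 limits them to description. This stands as a reason for modest priority. It does not justify having no analysis by assigned arm when SAP 5.1 estimates every difference between arms.

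A second answer is that received only tells each eye's own procedure apart from the patient's first allocation, because, as SAP 2.3 says, "Patients receiving subsequent CXL therapy were re-randomized". The sentence following the rule in SAP 3.2.2, on subjects appearing under different groups, fits that reading, and SAP 2.3 speaks of randomised treatment and treatment given as one thing. Loose wording is plausible. Still, every re-randomised procedure has its own assigned arm, so working by eye does not require grouping by receipt.

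A reader might infer three stronger points, which the documents do not support:

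- **That the arm differences are biased.** The treatment card carries the randomised group and the on/off cycle is automatic. No mismatch, and no link between mismatch and prognosis, is documented.
- **That an exact number of tables conflict.** The number depends on whether SAP 3.1 reaches the efficacy set.
- **That treatment received is undefined because the SAP names no CRF field.** The CRF and programming specifications are not among the documents, so this is only detail that may stand elsewhere.

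**Conclusion.** The concern holds in a limited form. As written, the pairwise efficacy contrasts are grouped by treatment received, with no analysis assigned specifically to the randomised arm and no count of mismatches. Tables 2.1 and 3 carry opposite rules, and the columns and denominators of Table 1 can refer to different groups.

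The effect on the estimates cannot be quantified, and it is zero if assigned and received arms always agree. The conclusion rests on the SAP text alone and assumes no particular mismatch rate. Because the results are descriptive and serve Phase 3 planning, priority is low to moderate.

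A reader might also infer that regrouping would give an intention-to-treat analysis. It would not. The efficacy set requires an observed change in at least one endpoint and excludes diagnosis mismatches (SAP 3.2.3), and not every patient returns at Month 12 (SAP 1.1).

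**What to change.** First confirm that the assigned arm is held in the database. SAP 3.1, 4.2 and 4.3 imply that it is, but SAP 2.1 reports that even the randomisation date has to be assumed. Then:

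- **SAP 3.2.3:** group each eye by the arm randomised for that eye's first procedure, with analysis by treatment received as supportive.
- **SAP 3.1:** say that efficacy and baseline summaries are by randomised arm and that Safety Analysis Set outputs are by treatment received.
- **SAP 3.2.1, 4, 4.1 and 4.2:** use the arm randomised for the primary eye's first procedure. In Table 1, show the Safety Analysis Set counts as a separately labelled block by treatment received, so that each block has one column definition.
- **SAP 4.3 (Table 3):** use treatment received, in line with SAP 3.2.2, which stays as it is.
- **Appendix B:** add one table of randomised against received arm, by eye.
- **SAP 3.2.3.1:** state that the regrouping does not make the efficacy set an intention-to-treat set.

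The cost is SAP wording, one small table and one repeated run by treatment received. If the cross-count shows no mismatches, the two runs coincide and the matter is closed.

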3.2.3.1 Justification for Exclusions

The results of the efficacy analysis are strictly to aid in program development. While the exclusions may limit generalizations with interpretation, they are in place to establish estimates

of a treatment effect at month 12 on the set of patients anticipated for the Phase III protocol. No hypotheses are being tested. Point estimates, standard errors, and confidence intervals are to be used for descriptive purposes only.

3.3 Strata and Covariates

Randomization will be stratified by indication and by investigational site. No strata or covariates will be considered in the planned analyses other than for establishing the subset needed for the EAS.

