3.8.2 Definition of Study Baseline

Study baseline is defined as the last observation obtained on or prior to the start of the procedure on the first eye on Study Day 1.

Change from baseline is defined as post-baseline assessment minus baseline assessment. Baseline value will not be carried forward to impute the post-baseline values.

For efficacy measures performed on individual eyes, baseline will be determined for each eye separately based on the date of the procedure on each particular eye.

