5.2 Secondary Endpoints

5.2.1 Uncorrected Visual Acuity

The primary analysis will be repeated for LogMAR of UCVA separately for each eye (primary eye and fellow eye).

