8.2 Appendix B: Tables, Listings, and Figures

Table 1	Disposition	Treated Analysis Set
Table 2.1	Demographics	Treated Analysis Set
Table 2.2	Demographics	Efficacy Analysis Set
Table 3	CXL Procedures	Safety Analysis Set
Table 4.1.1	Summary of Corrected Distance Visual Acuity	Efficacy Analysis Set
Figure 4.1.1	Mean +/- SE of Changes in Corrected Distance Visual Acuity	Efficacy Analysis Set
Table 4.1.2	Analysis of Changes in Corrected Distance Visual Acuity	Efficacy Analysis Set
Table 4.2.1	Summary of Corrected Distance Visual Acuity in Patients < 22 Years Old	Efficacy Analysis Set
Figure 4.2.1	Mean +/- SE of Changes in Corrected Distance Visual Acuity in Patients < 22 Years Old	Efficacy Analysis Set
Table 4.2.2	Analysis of Changes in Corrected Distance Visual Acuity in Patients < 22 Years Old	Efficacy Analysis Set
Table 4.3.1	Summary of Corrected Distance Visual Acuity in Patients with Baseline Kmax ≥ 47	Efficacy Analysis Set
Figure 4.3.1	Mean +/- SE of Changes in Corrected Distance Visual Acuity in Patients with Baseline Kmax ≥ 47	Efficacy Analysis Set
Table 4.3.2	Analysis of Changes in Corrected Distance Visual Acuity in Patients with Baseline Kmax ≥ 47	Efficacy Analysis Set
Table 5.1.1	Summary of Uncorrected Visual Acuity	Efficacy Analysis Set
Figure 5.1.1	Mean +/- SE of Changes in Uncorrected Visual Acuity	Efficacy Analysis Set
Table 5.1.2	Analysis of Changes in Uncorrected Visual Acuity	Efficacy Analysis Set
Table 5.2.1	Summary of Uncorrected Visual Acuity in Patients < 22 Years Old	Efficacy Analysis Set
Figure 5.2.1	Mean +/- SE of Changes in Uncorrected Visual Acuity in Patients < 22 Years Old	Efficacy Analysis Set
Table 5.2.2	Analysis of Changes in Uncorrected Visual Acuity in Patients < 22 Years Old	Efficacy Analysis Set
Table 5.3.1	Summary of Uncorrected Visual Acuity in Patients with Baseline Kmax ≥ 47	Efficacy Analysis Set
Figure 5.3.1	Mean +/- SE of Changes in Uncorrected Visual Acuity in Patients with Baseline Kmax ≥ 47	Efficacy Analysis Set
Table 5.3.2	Analysis of Changes in Uncorrected Visual Acuity in Patients with Baseline Kmax ≥ 47	Efficacy Analysis Set

Table 6.1.1	Summary of Maximum Corneal Curvature	Efficacy Analysis Set
Figure 6.1.1	Mean +/- SE of Maximum Corneal Curvature	Efficacy Analysis Set
Table 6.1.2	Analysis of Changes in Maximum Corneal Curvature	Efficacy Analysis Set
Table 6.1.3	Categorical Shifts in Maximum Corneal Curvature	Efficacy Analysis Set

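### Pairwise group differences come from an unadjusted ANOVA of change; adding each endpoint's own baseline needs no new data and will generally narrow the intervals

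*SAP*

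**What the plan says.** SAP 3.3 notes that randomisation was stratified by indication and site, then rules out any use of covariates: "No strata or covariates will be considered in the planned analyses other than for establishing the subset needed for the EAS". SAP 5.1 takes the change from baseline in LogMAR CDVA at each timepoint separately and adds: "ANOVA will also be used to obtain point estimates and CIs for all pairwise comparisons between the treatment arms". SAP 5.2 repeats this for UCVA and Kmax, for primary and fellow eyes. Appendix B carries it into the age and Kmax subgroups, for example the table titled "Analysis of Changes in Corrected Distance Visual Acuity in Patients < 22 Years Old".

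The planned sensitivity analysis, Satterthwaite t-tests, is also unadjusted. The only other model mentioned is that "mixed models repeated measures to account for the longitudinal nature of the data may be considered in an ad hoc manner", with no baseline term named.

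SAP 3.8.2 defines the outcome: "Change from baseline is defined as post-baseline assessment minus baseline assessment". It also provides that "baseline will be determined for each eye separately based on the date of the procedure on each particular eye". The baseline therefore exists for every value analysed. On purpose, SAP 3.2.3.1 says: "Point estimates, standard errors, and confidence intervals are to be used for descriptive purposes only".

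**The concern.** The deliverable is a set of estimates and intervals for planning Phase 3. With no hypothesis tested, what the arm comparisons can offer is precision and accuracy given the baselines that actually occurred. An unadjusted comparison of change gives up some of both unless the slope of follow-up on baseline is exactly 1. Randomisation was not stratified by baseline acuity or Kmax, so chance differences will arise, and each one moves the unadjusted estimate. Protocol 8.2 itself expects presenting severity to influence the size of the effect, which makes a slope of exactly 1 less plausible.

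The point concerns pairwise differences only. The within-group mean change, which SAP 5.1 makes the primary measure, is not criticised.

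**Working it through.** **Inputs.** Three arms (Protocol 3.4), assumed equal in size because no allocation ratio is stated. 95% intervals (SAP 5), taken as two-sided. No covariates (SAP 3.3). The documents give no SD, no baseline-to-follow-up correlation and no size for the efficacy set, and the 3,000 subjects in Protocol 8.2 have no effect size, SD or power behind them. There is thus no planned figure to reproduce, and r and k below are assumptions.

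**Precision.** Let r be the correlation and k the follow-up SD divided by the baseline SD. In units of the baseline variance:

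- variance of change: 1 + k² − 2rk
- ANCOVA residual variance: k²(1 − r²)
- difference between them: (1 − rk)², which is never negative and is zero only when the slope rk equals 1.

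Excess width of the unadjusted interval = √[(1 + k² − 2rk) / (k²(1 − r²))] − 1. Example, k = 1 and r = 0.7: √(0.60/0.51) − 1 = 8.5%.

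| k | r = 0.5 | r = 0.7 | r = 0.9 |
|---|---|---|---|
| 0.9 | 22.4% | 15.4% | 11.1% |
| 1.0 | 15.5% | 8.5% | 2.6% |
| 1.1 | 10.6% | 4.2% | 0.0% |

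**Cost in small arms.** Three-arm simulations included the lost degree of freedom and the estimated slope. Ratio of ANCOVA to ANOVA interval width at k = 1:

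| Eyes per arm | r = 0.5 | r = 0.7 | r = 0.9 |
|---|---|---|---|
| 8 | 0.888 | 0.947 | 1.002 |
| 15 | 0.877 | 0.934 | 0.987 |
| 30 | 0.871 | 0.928 | 0.980 |
| 100 | 0.868 | 0.924 | 0.976 |

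Unfavourable cases: with slope exactly 1 (r = 0.8, k = 1.25), the ratio is 1.029 at 8 per arm, 1.013 at 15 and 1.006 at 30. With r = 0.9 and k = 1.1, ANCOVA is about 0.9% wider at 20 per arm and 0.1 to 0.2% wider at 100. Overall coverage was about 95% for both methods.

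**Effect of a baseline difference.** A baseline difference d between two arms moves the unadjusted estimate by (rk − 1)d. At k = 1, a hypothetical 0.05 LogMAR difference moves it by 0.025, 0.015 or 0.005 in size at r = 0.5, 0.7, 0.9. For a difference of one standard error, the shift in standard errors of the estimate is √((1 − r)/2) = 0.50, 0.39, 0.22, whatever the arm size. With b = √((1 − r)/2) and s = √((1 + r)/2), the coverage of the unadjusted 95% interval given a baseline difference of m standard errors is Φ((1.96 − mb)/s) − Φ((−1.96 − mb)/s):

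| m | r = 0.5 | r = 0.7 | r = 0.9 |
|---|---|---|---|
| 0 | 97.6% | 96.6% | 95.6% |
| 1 | 95.2% | 95.1% | 95.0% |
| 2 | 86.6% | 89.9% | 93.3% |

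There are up to 3 pairs × 3 endpoints × 2 eyes × 3 populations = 54 baseline comparisons. By chance, 54 × 0.0455 ≈ 2.5 are expected to reach two standard errors. The comparisons overlap, so this is an expected count, not 54 separate risks.

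**Why the group means should stay unadjusted.** With three equal arms and k = 1, the usual ANCOVA standard error of an adjusted group mean, relative to the unadjusted one, is 0.866, 0.922 or 0.975, against a true 0.913, 0.949 or 0.983. Coverage falls to 93.7%, 94.3% or 94.8%.

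**The case against.** **No error is shown.** The planned contrast is a standard method, chosen openly, in a descriptive interim analysis whose primary measure is left alone. This stands, and it is why the point is an improvement and not a fault.

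**The gain is assumed.** No document supplies r or k, and with equal SDs the excess falls to 1.3% at r = 0.95 and 0.5% at r = 0.98. This stands. The range is the honest answer, and Kmax could sit at the low end.

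**Unadjusted coverage fails only at larger imbalances.** True: it is at or above nominal up to about one standard error, as the table shows.

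**The subgroups are where adjustment helps least.** This stands in part. Smaller arms have larger absolute imbalances, but the shift in standard errors does not grow, and very small arms are where ANCOVA can cost 2 to 3%. In the Kmax ≥ 47 subgroup, the Kmax baseline is truncated. If the baseline is normal and cut at its median, with r = 0.7 and k = 1, its variance falls to 1 − 2/π = 0.363. The excess is then √((0.09 × 0.363 + 0.51)/0.51) − 1 ≈ 3%, against 8.5% untruncated.

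**The efficacy set is not a clean randomised comparison.** SAP 3.2.3 excludes patients after randomisation and analyses by treatment received, and SAP 1.1 says not everyone returns at Month 12. Unbiasedness is therefore not strictly assured for either method, and if selection causes the baseline differences, the two can estimate different quantities. This stands. It is a reason to show both results.

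**ANCOVA assumes a common slope, and unadjusted means will not subtract to adjusted differences.** Both are true; a check and a footnote deal with them.

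**Conclusion.** The concern holds as a free improvement. Nothing in either document brings the baseline into the pairwise comparisons, and the value is already in every change score. In large samples with a common slope, adjustment cannot lose precision, and it gains unless the slope is exactly 1. Over the assumed values (r from 0.5 to 0.9, SD ratio from 0.9 to 1.1), the unadjusted intervals are 0 to 22.4% wider than the adjusted ones. The possible loss is about 1% at 20 eyes per arm and 2 to 3% at about 8, when the slope is near 1. No claim about type I error or power is affected. Confidence in the size is moderate, because it rests on assumed correlations and SDs, equal arms and a common slope. Confidence in the direction is higher.

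**What to change.** Before the interim database lock:

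- **SAP 3.3:** state that pairwise treatment differences are adjusted for the baseline of the endpoint and eye analysed, and that no other covariate is planned.
- **SAP 5.1:** at each timepoint, take the pairwise differences in LogMAR CDVA and their 95% intervals from ANCOVA with treatment group and baseline LogMAR CDVA.
- **SAP 5.2:** use the same model for LogMAR UCVA and Kmax, each with its own baseline.
- Report the residual SD for Phase 3 planning, and check the common-slope assumption, especially if arms are unequal.
- Keep the unadjusted within-group mean changes and intervals as the headline, with a footnote that they will not subtract exactly to the adjusted differences.
- Keep the unadjusted ANOVA and the Satterthwaite t-tests as supportive. They guard against very small subgroup arms and cover unequal variances.

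Site need not be added: its gain is unproven, and fixed terms for 21 sites could cost precision in a small efficacy set.

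The cost is SAP wording, one model term and revised shells for the nine analysis-of-change tables in Appendix B. No new data are needed.
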